- Was the test request form returned to Cairn in the mailer with the breath samples?
- Was the patient demographic information (including units) entered correctly on the form?
- Were pre-meal breath sample collection times recorded appropriately?
- Were meal start/end times recorded appropriately?
- Were post-meal breath sample planned and actual sample collection times calculated/recorded appropriately?

6.4.8 Patient ability to collect GEBT breath samples under the supervision of a telehealth professional

Ability to collect GEBT breath samples will be assessed by examination of GEBT results for participants (ensure adequate CO_2 in each sample/delta values follow expected pattern if collected in correct order). In addition, patients will be asked about instruction on breath sample collection.

6.4.8.1 Patients will be asked whether instructions of collecting breath samples were easy to follow (Exhibit B).

6.4.8.2 Cairn Telehealth personnel will review breath samples over the telehealth platform and note whether condensate is observed in breath tubes (Exhibit C)

(Note: breath condensate is not always visible in breath tubes, even when a sample has been collected successfully, this data is being collected for information only)

6.4.8.3 Cairn Clinical Laboratory personnel will review breath tubes received and GEBT results obtained to determine whether breath samples were collected correctly as follows (Exhibit D):

- Is condensate visible in breath tubes (see note above)?

- Does each breath sample contain a minimum of 1%CO₂ (in the case of pre-meal samples, at least one sample must contain a minimum of 1% CO₂)?
- Did the breath samples appear to have been collected in the correct order? (In correctly collected samples sets, pre-meal sample delta values will (usually) be more negative than post-meal delta values and post-meal delta values tend to increase in value over time – in normal patients, they may start to decline after 120 minutes – and in delayed patients rise to a maximum at 240 minutes).

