6.5.2 Safety of telehealth administration of ^{13}C -Spirulina GEBT

There are no more/more severe adverse events than would have been expected to occur during in-office administration of ^{13}C -Spirulina GEBT.

6.5.3 Patient ability to prepare and administer the ^{13}C -Spirulina GEBT, under the supervision of a telehealth professional, according to instructions

Greater than or equal to 90% of Patient questionnaires record no issues with meal preparation (Exhibit B, Section 4)

Greater than or equal to 90% of meal preparation steps (described in Exhibit C, section 1) were completed successfully.

6.5.4 Patient ability to complete the GEBT test request form, under the supervision of a telehealth professional, according to instructions

Errors in test request forms occur at a rate of ~16% for in-office test administration. There are no more errors in test request form completion than are routinely found in test request forms returned with GEBTs administered in office.

6.5.5 Patient ability to collect GEBT breath samples under the supervision of a telehealth professional

Missing breath samples occur at a rate of ~6% for in-office test administration. There is not a higher incidence of missing breath samples in breath samples collected via telehealth than are routinely found in breath samples returned from GEBTs administered in office.

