6.6 End of Study

- Participants may withdraw from the study at any time, without prejudice
- An authorized investigator may discontinue any test subject at any time if medically indicated or in the best interest of the individual
- Participants who do not complete all components of the testing and compliance procedures will be excluded from the statistical analysis
- Withdrawn participants may be replaced to achieve the number of subjects specified
- The trial may be terminated prematurely if, in the judgement of Cairn's Medical Director, the severity or frequency of adverse events so warrants

Each participant is considered to have completed the study when they have completed the GEBT test administrations, follow-up questionnaire and AE review follow-up and all collected breath samples have been analyzed on the ABCA GIRMS system.

The end of the study is defined as the date on which all of the participants' breath samples have been analyzed on the ABCA GIRMS, all participant's study questionnaires have been returned, and all follow-up (AE review) has been completed.

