3.0 TELEHEALTH PLATFORM

Did the patient appear to have trouble using the telehealth platform? Yes No

If no, please describe what was difficult to use: _____

Did the telehealth session fail at any time during your test? Yes No

If yes, please explain: _____

Did you lose internet connection at any point during the test? Yes No

What kind of internet connection were you using for the telehealth administration of GEBT?

Cable DSL Satellite Cellular Other (Describe: _____) Don't know

Patient ID: _____

GEBT ID: _____

1.0 TEST REQUEST FORMWas the completed test request form returned with the GEBT breath samples? Yes No Was patient height recorded? Yes No Units entered? Yes No Was patient weight recorded? Yes No Units entered? Yes No Was patient sex recorded? Yes No Was patient age recorded? Yes No Were the pre-meal breath sample collection times entered? Yes No Was the meal start time entered? Yes No Was the meal end time entered? Yes No Were all post-meal planned breath sample collection times calculated correctly? Yes No Were all post-meal actual breath sample collection times entered? Yes No

Post-meal collection time	Post meal planned collection time	Post meal actual collection time	Actual time +/- 5 mins of planned time?
45 minutes	Yes  No 	Yes  No 	Yes  No 
90 minutes	Yes  No 	Yes  No 	Yes  No 
120 minutes	Yes  No 	Yes  No 	Yes  No 
150 minutes	Yes  No 	Yes  No 	Yes  No 
180 minutes	Yes  No 	Yes  No 	Yes  No 
240 minutes	Yes  No 	Yes  No 	Yes  No 

2.0 BREATH SAMPLE COLLECTIONWas condensate visible in the breath tubes received? Yes No Did the breath samples contain sufficient CO₂ (i.e., >1% CO₂)

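### Breath collection is assessed by CO2 content, but acceptance rule 6.5.5 limits only undefined missing samples, so returned tubes with too little CO2 may face no limit

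*Protocol*

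**What the plan says.** **Assessment.** Protocol 6.4.8 states: "Ability to collect GEBT breath samples will be assessed by examination of GEBT results for participants". It names adequate CO2 in each sample and a plausible delta pattern as what will be examined. Section 6.4.8.3 gives the laboratory checks. Each sample needs at least 1% CO2, relaxed before the meal: "in the case of pre-meal samples, at least one sample must contain a minimum of" 1%. The second check is on order: "Did the breath samples appear to have been collected in the correct order". Visible condensate is noted too, but 6.4.8.2 treats it as information only.

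**Recording.** Exhibit D section 2.0 asks "Did the breath samples contain sufficient" CO2, with a yes/no for one pre-meal row and six post-meal rows.

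**Acceptance.** Section 6.5.5 gives the benchmark, "Missing breath samples occur at a rate of ~6% for in-office test administration", and the rule: "There is not a higher incidence of missing breath samples in breath samples collected via telehealth" than is routine among samples returned from in-office tests. It neither defines a missing sample nor gives the unit of the 6%.

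**Analysis set.** Section 6.6 adds: "Participants who do not complete all components of the testing and compliance procedures will be excluded from the statistical analysis". The same section counts a participant as complete once, among other things, all samples that were collected have been analyzed.

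**The concern.** The section that says how collection will be judged and the rule that decides pass or fail measure different things. The synopsis undertakes to show that remote supervision is adequate for proper collection of breath samples, and 7.1 warns that collection errors can affect results and make retesting necessary. A tube that comes back with too little CO2 is a collection failure by the protocol's own check, yet the acceptance rule does not clearly count it.

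This matters more for remote collection. Under SOP-CD-028 (3.5.4, 3.6.1 and the call script in its Exhibit B), the first video call ends once the post-meal times have been planned. The six post-meal samples are then prompted by text message, and video resumes only after the 240-minute sample. The final call looks at the tubes for condensation, which 6.4.8.2 says may be absent even after a good collection. CO2 content is therefore the protocol's objective check that these samples are adequate.

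**Working it through.** **1. Is there anything to reproduce?** No. The in-office rate of about 6% comes without numerator, denominator or source, and the protocol derives no sample size from it.

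**2. Does any criterion in 6.5 limit low CO2?**

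| Section | What it limits | Limits low CO2? |
|---|---|---|
| 6.5.1 | subgroup sizes | no |
| 6.5.2 | adverse events | no |
| 6.5.3 | meal preparation | no |
| 6.5.4 | test request form errors | no |
| 6.5.5 | missing breath samples | only if low CO2 counts as missing |
| 6.5.6 | delivery, return, 28-day window | no |
| 6.5.7 | telehealth platform | no |

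**3. What follows if low CO2 does not count as missing?** With no tube missing, the observed missing rate is 0%, and 6.5.5 is met whatever the CO2 results are. In the extreme, all 30 of 30 or 50 of 50 tests could have inadequate CO2. This shows what the wording permits; it is not a forecast.

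**4. What does Exhibit D capture?** As printed, it records CO2 at 1 + 6 = 7 time points. It has no item for whether each tube was returned, which 6.5.5 needs on the narrow reading, and no order item, although 6.4.8.3 assigns that check to it. The CO2 wording also differs slightly: 6.4.8.3 asks for a minimum of 1%, Exhibit D for more than 1%.

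**5. How much does the unit matter?** Inputs: 30 to 50 participants (section 5.0), one test each (6.4.2), 2 pre-meal and 6 post-meal tubes (Table 1), so 8 tubes per test. Assumption: about 6% is read as a ceiling on the observed rate, because 11.4 leaves the comparison method open. Largest count allowed = floor(0.06 × N).

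| Unit | 30 participants | 50 participants |
|---|---|---|
| Test | 0.06 × 30 = 1.8 → 1 of 30 | 0.06 × 50 = 3.0 → 3 of 50 |
| Time point (7 per test) | 0.06 × 210 = 12.6 → 12 of 210 | 0.06 × 350 = 21.0 → 21 of 350 |
| Tube (8 per test) | 0.06 × 240 = 14.4 → 14 of 240 | 0.06 × 400 = 24.0 → 24 of 400 |

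On the tube reading, 14 missing tubes touch between 2 tests (14/8 = 1.75, rounded up) and 14 of 30; 24 missing tubes touch between 3 (24/8) and 24 of 50. The benchmark is approximate, so the exact cut-offs (1 against 2 of 30, for example) should not be pressed. The point is the gap between units.

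**The case against.** **Low-CO2 tubes may already count as missing.** Section 6.5.5 speaks of samples found missing among those returned, which fits an empty or inadequate tube. The tubes come with the kit, so an uncollected sample can come back as an empty tube, and the CO2 column is the only per-tube evidence of a sample on Exhibit D. This is a fair reading and may be the sponsor's practice. It stands to this extent: a reader might infer that 6.5 certainly sets no limit on low CO2, and the document does not support that. It leaves the matter open.

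**The unit may be set elsewhere.** An unseen SAP could fix it, and the wording of 6.5.5 leans towards counting per sample. On its own, the unit would be a minor point. The mismatch between 6.4.8.3 and 6.5.5 is different, because the pass/fail rule itself is fixed in the protocol.

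**The exclusion in 6.6.** A reader might infer that 6.6 removes every participant with a missing tube and so empties 6.5.5 of the cases it should count. The text does not establish this. Completion is tied to samples that were collected, not to all eight tubes, and the exclusion stands among bullets on withdrawal and replacement. Yet it speaks of all components of testing, so it can be read either way.

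**Order.** Section 6.4.8.3 hedges the expected delta pattern, so the lack of a pass/fail limit on order is not itself a defect.

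**Conclusion.** The concern holds in conditional form. The protocol assesses collection by CO2 content and records it, but its only acceptance rule for collection limits missing samples without saying whether inadequate ones are included. If they are not, 6.5.5 can be met with returned samples that fail the protocol's own adequacy check, and the claim of proper collection goes untested. How often that would happen cannot be estimated, because the protocol gives no in-office or expected rate of low CO2.

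The unit adds to the ambiguity: between counting tests and counting tubes, the allowed number differs 14-fold at 30 participants (14 against 1) and 8-fold at 50 (24 against 3), on the assumption of an observed ceiling of 6%. This should be fixed before the data are reviewed.

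**What to change.** 1. In 6.5.5, state whether tubes or time points below the 6.4.8.3 CO2 minimum count as missing, and use the same definition and unit as the in-office figure of about 6%.
2. If they do not count as missing, add a separate criterion from the existing Exhibit D data: the proportion of tests (or time points) that meet the 6.4.8.3 CO2 minimum must reach a limit fixed and justified before data review. Count each tube once, as missing or as insufficient.
3. In 6.6, state that every participant who was administered the GEBT stays in the 6.5.5 denominator, even if a tube is missing or insufficient.
4. Add to Exhibit D a tube-returned item and the order item that 6.4.8.3 assigns to it, and align the CO2 wording of the two. Report order descriptively.

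**Cost.** Protocol wording and two form items; CO2 is already recorded, so no new measurement is needed. The sponsor must check how the in-office 6% was counted. If a separate criterion is needed, the sponsor must also justify its limit, for which the protocol supplies no in-office rate. The reported success rate may be lower than with missing tubes alone.

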6.5.6 Ability to successfully ship kits/breath samples to/from home

Kits are delivered/received by subjects in time for the scheduled breath test and breath samples and test request form are returned to Cairn/analyzed within the 28-day stability period of breath samples.

6.5.7 Ability of a telehealth platform to function correctly

There are no significant problems with the telehealth platform: majority of users find the telehealth platform to be simple to use and do not have issues with internet access.

6.6 End of Study

- Participants may withdraw from the study at any time, without prejudice
- An authorized investigator may discontinue any test subject at any time if medically indicated or in the best interest of the individual
- Participants who do not complete all components of the testing and compliance procedures will be excluded from the statistical analysis
- Withdrawn participants may be replaced to achieve the number of subjects specified
- The trial may be terminated prematurely if, in the judgement of Cairn's Medical Director, the severity or frequency of adverse events so warrants

Each participant is considered to have completed the study when they have completed the GEBT test administrations, follow-up questionnaire and AE review follow-up and all collected breath samples have been analyzed on the ABCA GIRMS system.

The end of the study is defined as the date on which all of the participants' breath samples have been analyzed on the ABCA GIRMS, all participant's study questionnaires have been returned, and all follow-up (AE review) has been completed.

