11.4 Statistical Analysis

Comparisons of rates of occurrence of errors in test administration procedures between telehealth and in-office administered tests will be performed according to accepted statistical techniques.

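### The completeness exclusion in Protocol 6.6, read plainly, removes participants with an uncollected breath sample from the comparison meant to count them, and biases criterion 6.5.5 toward a pass

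*Protocol*

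**What the plan says.** Section 6.6 (End of Study) fixes who is analysed: "Participants who do not complete all components of the testing and compliance procedures will be excluded from the statistical analysis". The next bullet adds: "Withdrawn participants may be replaced to achieve the number of subjects specified". The protocol does not define the components or name any other analysis set.

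The same section then defines study completion by two conditions. One concerns the participant's own tasks: "completed the GEBT test administrations, follow-up questionnaire and AE review follow-up". The other concerns the laboratory work: "all collected breath samples have been analyzed on the ABCA GIRMS system".

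Section 11.4 describes one analysis: "Comparisons of rates of occurrence of errors in test administration procedures between telehealth and in-office administered tests". That comparison serves criteria 6.5.4 and 6.5.5. For 6.5.5 the benchmark is: "Missing breath samples occur at a rate of ~6% for in-office test administration". The telehealth incidence must be no higher "than are routinely found in breath samples returned from GEBTs administered in office". Criterion 6.5.4 has the same form, with errors no more frequent "than are routinely found in test request forms returned with GEBTs administered in office". Both benchmarks therefore describe returned material.

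Section 6.1 (Visit 2) makes the pre-meal samples and six post-meal samples part of the test. Section 5.0 sets 30 to 50 participants.

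**The concern.** Criterion 6.5.5 asks whether patients can collect their breath samples at home, and the event that answers it is a sample not collected. If a participant with that event has not completed every component, section 6.6 removes them before the rate is calculated. Membership of the analysis set then depends on the outcome being measured, always in the favourable direction for this event.

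The second difficulty is that section 6.6 offers two standards of completion without linking them. One governs the analysis set and requires all components. The other governs study completion and requires only that the samples actually collected be analysed. A participant with one uncollected tube can meet the second and fail the first. Someone applying the protocol after the data are in could keep or drop that participant, and the choice can decide whether an acceptance criterion is met. Under section 14.0 these data are to demonstrate usability, so the choice matters.

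**Working it through.** The protocol gives no sample-size, power or alpha figure to reproduce. The check has a logical part and a numerical illustration.

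**1. What each reading does to a participant with one uncollected tube**

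| Reading of section 6.6 | Participant | Effect on 6.5.5 |
|---|---|---|
| Plain wording: each scheduled sample is a component | Excluded | The uncollected sample leaves numerator and denominator |
| Completion definition: only collected samples need analysis | Kept | The uncollected sample is counted |
| Dropouts only | Kept | Counted; abandoned tests and unreturned kits are removed |

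Same data under the first two readings (assumed example: 4 of 32 participants each miss one sample): 4/32 = 12.5%, above 6%; or 0/(32 − 4) = 0/28 = 0%, below 6%.

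**2. Inputs for the illustration**
- From the protocol: benchmark 6% (6.5.5); n = 30 or 50 (5.0).
- Assumed: 6% is per participant, because the protocol does not say per participant or per tube; independent participants; a true telehealth rate of 20%; a one-sided 5% exact binomial test against 6%, because 11.4 names no test.

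**3. Telehealth exactly as good as in office (true rate 6%)**
- Expected number with a missing sample: 30 × 0.06 = 1.8; 50 × 0.06 = 3.0.
- Probability that at least one is removed: 1 − 0.94^30 = 0.844; 1 − 0.94^50 = 0.955.

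So the rule would probably be triggered even if telehealth were no worse. This step takes every missing sample to be an uncollected one.

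**4. Telehealth clearly worse (assumed true rate 20%)**
- Critical count, the smallest c with P(X ≥ c | n, 0.06) ≤ 0.05: c = 5 for n = 30 (size 0.032); c = 7 for n = 50 (size 0.029).
- Power counting everyone: P(X ≥ 5 | 30, 0.20) = 0.745; P(X ≥ 7 | 50, 0.20) = 0.897.
- With the plain exclusion, the expected 6 of 30 or 10 of 50 affected participants are removed, and uncollected samples add nothing to X.

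**5. If 6% is per tube**
With independent tubes, the chance that a participant has at least one missing is 1 − 0.94^6 = 0.31 for six tubes and 1 − 0.94^8 = 0.39 for eight. The exclusion would then remove about 9 to 12 of 30, or 16 to 20 of 50. The direction is the same and more participants are affected.

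**6. Dropout-only reading**
Removing abandoned tests and unreturned kits favours a pass for those events. Removing participants who returned a full kit but missed only the follow-up acts the other way. Assumed example: 2/34 = 5.9% becomes 2/30 = 6.7% when four such participants are dropped. This takes the follow-up at Visit 3 as in section 6.1; section 6.4.6 instead has the questionnaire returned with the samples, but the adverse-event contact remains a separate step.

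**The case against.** The strongest reply is that the bullet was never meant to catch a missed tube. It stands between investigator discontinuation and replacement of withdrawn participants, so it can be read as concerning dropouts. The completion definition that follows can be taken to explain the undefined word. Other parts of the protocol fit this: section 6.4.8.3 accepts one adequate pre-meal sample, and Exhibit D records incomplete times and inadequate samples as outcomes. A reading that leaves 6.5.5 with little to measure is unlikely to be what the sponsor intended.

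This has force as to intent, and it is why the two statements are better described as in tension than as contradictory: they serve different functions and collide only if each tube is a component. It does not remove the problem. The bullet is not limited to withdrawal, nothing exempts 6.5.5, and an analysis plan that kept these participants under the plain reading would depart from the protocol.

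A reader might also infer that 6.5.5 cannot fail, or that the missing-sample count is zero by construction. The documents do not support that. A participant who collected every sample but lost one in return shipping has completed the procedures and would still count. Section 6.5.5 does not define missing, so samples with too little CO2 might count as well. The claim is limited to uncollected samples under the plain reading. Nor is any bias claimed for 6.5.6 or 6.5.7: shipping dates are recorded separately (6.4.9.3) and 6.5.7 asks only for a majority.

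**Conclusion.** The concern holds in this form: on its plain wording, section 6.6 takes uncollected breath samples out of the comparison that 6.5.5 relies on and biases the criterion toward a pass. The completion definition in the same section points the other way, so the result can depend on which standard is applied.

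The direction under the plain reading depends neither on the test chosen nor on the unit of the 6%. The probabilities do. They rest on the per-participant unit and, for the power figures, on the assumed 20% rate and exact test. On the dropout-only reading the effect is smaller and not one-directional. The wording should be settled before the data are analysed, because 6.5.5 is a stated acceptance criterion.

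**What to change.** Replace the bullet in section 6.6 with wording to this effect:

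*For 6.5.4 and 6.5.5 the analysis includes every participant who starts the GEBT and returns a kit, to match the returned-kit in-office benchmarks. An uncollected or missing breath sample, or a missing or incomplete test request form, counts as an error and is never a reason for exclusion. Missing follow-up does not remove a participant from these criteria. Participants who abandon the test or do not return a kit are listed with reasons and counted as failures in a sensitivity analysis. A completers-only analysis is supportive.*

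Also state in 6.5.5 whether the 6% is per participant or per tube, and use the same unit for telehealth.

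The cost is one paragraph of protocol text, with no extra participants or data. Reported rates may be slightly less favourable. If the criterion were judged on the raw rate alone (an assumption), counting everyone means that a telehealth rate truly equal to 6% would still exceed the benchmark by chance with probability 1 − 0.456 = 0.54 (n=30, 2 or more) or 1 − 0.647 = 0.35 (n=50, 4 or more). The sponsor should know this when choosing the comparison under 11.4; it does not justify keeping the exclusion.
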